## **11.2** Calculation or derivation of safety variable(s)

## 11.2.1 Adverse events

A treatment-emergent adverse event (TEAE) is defined as any AE that started on or after the first dose of study drug up to the last dose of study drug. An AE already present at the time of the first dose of study drug that worsens in intensity following exposure to study drug or an AE with an unknown/not reported onset date will also be considered as treatment-emergent. Adverse events occurring after the last dose of study drug will also be summarized, which among other purposes, may assess any potential withdrawal-type effects.

Time to onset of an AE (in days) will be calculated as:

AE start date - Date of the first dose of study drug + 1.

Duration of an AE (in days) will be calculated as:

AE resolution date - AE start date + 1.

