## 11.2.12 C-SSRS

Occurrence of suicidal behavior after baseline up to the final assessment (Week 14) will be defined as having answered "yes" to at least 1 of the 4 suicidal behavior sub-categories (actual attempt, interrupted attempt, aborted attempt, and preparatory acts or behavior) at any post-baseline evaluation.

Occurrence of suicidal ideation after baseline up to the final assessment (Week 14) will be defined as having answered "yes" to at least 1 of the 5 suicidal ideation sub-categories (wish to be dead, non-specific active suicidal thoughts, active suicidal ideation with any methods [not plan] without intent to act, active suicidal ideation with some intent to act [without specific plan], and active suicidal ideation with specific plan and intent) at any post-baseline evaluation.

The primary baseline C-SSRS values will be defined as the latest non-missing value collected prior to the first dose of study drug in the previous pivotal study (D3820C00004) (screening, Visit 1 or Week 0, Visit 3), and supportive baseline C-SSRS values will be defined as the data collected at Visit 8 from the previous study D3820C00004 (also defined as Visit 1 of this study).

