All laboratory test results, vital signs (sitting blood pressure and pulse), ECG results, body temperature, respiratory rate, and weight will be summarized for each treatment group using descriptive statistics at each visit for observed values and change from baseline.

The overall incidence, as well as shifts from baseline to each post-baseline visit, of potentially clinically significant laboratory test results, vital signs, ECG results, body temperature, respiratory rate, and weight will be summarized by treatment group. For visits where triplicate ECGs are obtained, the mean value of the 3 measurements will be used in the analysis.

Physical examination results (normal/abnormal by body system) will be summarized for each visit by treatment group. Changes from baseline in the physical examination results will be assessed using shift tables.

The proportion of patients with suicidal behavior and suicidal ideation throughout the study based on the C-SSRS will be presented for each treatment group. The proportion of patients within each of the 4 suicidal behavior categories and within each of the 5 suicidal ideation sub-categories will also be presented for each treatment group. Descriptive statistics on the total number of attempts, total number of interrupted attempts, and total number of aborted attempts will be summarized for each treatment group.

Total exposure to NKTR-118 12.5 and 25 mg will be summarized combining the data from the current study with the exposure data from the previous pivotal study (D3820C00004).

Safety parameters may also be summarized by age group, gender, race, region, and response to laxatives (LIR, non-LIR), as appropriate.

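### The C-SSRS ideation count is not compared with either defined baseline, so persisting ideation is pooled with new onset and worsening is not shown

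*Protocol*

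**What the plan says.** Protocol Section 11.2.12 gives the derivation in full: "Occurrence of suicidal ideation after baseline up to the final assessment (Week 14) will be defined as having answered" yes to one or more of the five ideation sub-categories "at any post-baseline evaluation". Suicidal behavior has a parallel rule with four sub-categories.

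The same section then sets two reference points. "The primary baseline C-SSRS values will be defined as the latest non-missing value collected prior to the first dose of study drug" in the pivotal study, and "supportive baseline C-SSRS values will be defined as the data collected at Visit 8 from the previous study D3820C00004".

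The analysis in Section 12.2.1 is: "The proportion of patients with suicidal behavior and suicidal ideation throughout the study based on the C-SSRS will be presented for each treatment group". It adds the proportion in each sub-category and descriptive counts of attempts.

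Other safety data in the same protocol are tied to the patient's starting state:
- Section 11.2.1 lets an existing event become treatment-emergent only on deterioration: "An AE already present at the time of the first dose of study drug that worsens in intensity following exposure to study drug".
- Section 12.2.1 says of physical findings: "Changes from baseline in the physical examination results will be assessed using shift tables". It also plans shifts from baseline for laboratory tests, vital signs and ECG.

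**The concern.** The ideation rule looks only at answers after baseline. Two baselines are defined directly below it, but no sentence in Section 11.2.12 or 12.2.1 uses them to judge those answers. Three different patients therefore look alike in the top-line row:
- one with the mildest category before treatment and the same category throughout;
- one with no ideation at baseline who develops it in the study;
- one who moves from the mildest category to the most severe.

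The sub-category proportions separate the third patient by severity, but they are marginal. They show how many patients were in each category, not who moved up from where they started.

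Section 3.2 says the C-SSRS is there to assess suicidality risk, and Section 2.1 makes comparison with placebo on safety the primary objective, by descriptive statistics. With no test or model to take baseline into account, the tabulated proportion is itself the comparison. What it counts therefore decides what can be learned.

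**Working it through.** The protocol states no C-SSRS rate and no sample size calculation, so there is no figure of its own to reproduce. The check has a reading part and an illustration.

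**Reading**

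1. Does the occurrence rule use a baseline value? No. Any yes after baseline is enough (Section 11.2.12).
2. Does the analysis section add a comparison? No. It lists proportions and counts of attempts, with no shift table or new-or-worse category for the C-SSRS (Section 12.2.1).
3. Does the general baseline text in Section 12.2 add one? It plans change from both baselines for safety parameters only where that is suitable, and Section 11.2.12 defines no C-SSRS change variable for it to act on.
4. Can patients with baseline ideation enter? No criterion listed in Section 4.2 excludes a positive C-SSRS ideation answer. Exclusion 6 covers psychiatric conditions that put the patient at undue risk, with inadequately controlled depression as an example. Section 4 also applies the pivotal study's criteria. Baseline prevalence is thus unknown and may be low, but it is not shown to be zero.

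**Illustration (all rates assumed)**

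Let b be the share of patients with ideation at baseline, s the probability that it is reported again later (equal in both arms), and p the new-onset rate among the rest. The rule counts

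b × s + (1 − b) × p.

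Take p = 1% on placebo and 3% on active drug, so the new-onset ratio is 3.0 and the difference 2.0 points. For b = 5% and s = 100%:
- placebo: 0.05 + 0.95 × 0.01 = 5.95%
- active: 0.05 + 0.95 × 0.03 = 7.85%
- ratio 7.85 / 5.95 = 1.32; difference 1.90 points
- share of active-arm cases already present at baseline: 5.00 / 7.85 = 64%

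| b | s | Placebo | Active | Ratio | Difference (points) |
|---|---|---|---|---|---|
| 1% | 50% | 1.49% | 3.47% | 2.33 | 1.98 |
| 1% | 100% | 1.99% | 3.97% | 1.99 | 1.98 |
| 2% | 50% | 1.98% | 3.94% | 1.99 | 1.96 |
| 2% | 100% | 2.98% | 4.94% | 1.66 | 1.96 |
| 5% | 50% | 3.45% | 5.35% | 1.55 | 1.90 |
| 5% | 100% | 5.95% | 7.85% | 1.32 | 1.90 |
| 10% | 50% | 5.90% | 7.70% | 1.31 | 1.80 |
| 10% | 100% | 10.90% | 12.70% | 1.17 | 1.80 |

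The b × s term cancels in the difference, which is 2.0 × (1 − b).

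**Worsening**

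Keep b = 5% and s = 100%, and suppose 5% of baseline-positive patients worsen on placebo and 20% on active drug.
- New or worse, placebo: 0.05 × 0.05 + 0.95 × 0.01 = 1.20%
- New or worse, active: 0.05 × 0.20 + 0.95 × 0.03 = 3.85%
- Ratio 3.85 / 1.20 = 3.2; difference 2.65 points

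The protocol's rule still gives 5.95% and 7.85%, a ratio of 1.3 and a difference of 1.90 points. The worsening part, 0.05 × (0.20 − 0.05) = 0.75 points, is absent, because those patients already count in both arms.

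**The case against.** Several objections have weight.

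**The any-yes proportion is a coherent summary, and a shift table could be left to the SAP.** True of the table. But the protocol itself fixes the derivation and defines two baselines beside it without using them. It is reasonable to close that gap where the rule is written.

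**Suicidality is already captured with reference to baseline.** Section 6.3.4 says suicidal thoughts and preparation for suicide are to be regarded as adverse events, so the treatment-emergent rule applies to them. A reader might infer from the C-SSRS sections that new or worsened suicidality is summarized nowhere. The protocol does not support that. The safeguard is partial, because worsening of an adverse event is judged on mild, moderate or severe intensity and not on C-SSRS category.

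**Behavior is different.** A reader might extend the point to behavior with equal force. Section 6.3.14.1 refers to behavior since the previous visit, so a later yes would normally be a new act and not a persisting state. The point should stay mainly with ideation.

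**The dilution depends on the scale.** Persisting cases should balance between randomized arms, and the expected difference barely moves. The protocol specifies no risk ratio and no testing. This stands for new onset, but it does not rescue worsening.

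**Stakes are limited.** The C-SSRS is not in the list of safety variables in Section 6.3.1; it appears under other safety assessments. This also stands.

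**Conclusion.** The point holds for ideation. The rule pools persisting with new ideation and does not show worsening from the patient's own baseline category, although both baselines are defined. The sub-category proportions and the adverse-event route soften this but do not replace the missing comparison.

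Its size cannot be known from the protocol. Under assumed new onset of 1% against 3%, baseline prevalence of 1% to 10% and persistence of 50% to 100%, equal in both arms, a ratio of 3.0 shows as about 2.3 to 1.2. The expected difference stays at 1.8 to 2.0 points. Worsening among baseline-positive patients is lost on any scale.

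Two stronger readings go too far. One is that the rule hides a new-onset effect on every scale; the nearly constant difference contradicts it. The other is that the latest pre-dose value is the wrong baseline and the worst should replace it; nothing in the protocol shows that.

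**What to change.** Keep the any-yes proportion. In Section 11.2.12, define new-onset ideation (none at baseline, at least one category afterwards) and worsened ideation (a higher category than at baseline). In Section 12.2.1, report the proportion with new-onset or worsened ideation by arm, with a shift table from baseline category to worst post-baseline category. Do this against each of the two baselines as the protocol already defines them.

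All the data are already collected. The cost is a short addition to each section and one extra table, whose counts will be small and should be read as such.

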# **11.3** Calculation or derivation of patient reported outcome variables

## 11.3.1 PAC-SYM

See Section 11.1.1.

## 11.3.2 PAC-QOL

See Section 11.1.2.

## 11.3.3 NRS for Pain

See Section 11.2.2.

#### 11.3.4 Daily opioid dose

See Section 11.2.3.

## 11.3.5 Mean Bisacodyl dose per week

See Section 11.2.4.

## 11.3.6 EQ-5D

See Section 11.6.1.

## **11.4** Calculation or derivation of PK variables (Not applicable)

# 11.5 Calculation or derivation of pharmacodynamic (PD) variable(s) – (Not applicable)

## **11.6** Calculation or derivation of health economic variables

## 11.6.1 EQ-5D

The weighted health status index scores, derived from the 5 EQ-5D questions, will be calculated, summarized, analyzed, and reported outside of the main study report.

## 11.6.2 Healthcare resource utilization

Healthcare resource utilization will be assessed as the number of healthcare visits per patient year for the management of their OIC, which will be calculated as follows:

(total number of visits/number of days on study drug) x 365.25

The healthcare resource utilization will be summarized by type of OIC healthcare utilization category (physician or other health care practitioner, urgent care center or hospital ER, inpatient hospital).

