#### 3.1.3 Final Visit (Visit 5, Week 14, Day 99)

Visit 5 will occur on Day 99 ( $\pm$ 3 days). At Visit 5, the following procedures will be performed:

- PAC-SYM will be completed.
- PAC-QOL will be completed.
- EQ-5D will be completed.
- OIC Healthcare Resource Utilization questionnaire will be completed.
- Sitting blood pressure and pulse must be measured. Please see Section 6.3.13.1 for additional details on the protocol-mandated methods for collection of vital signs. The accurate time in date, hours and minutes will be recorded for this measurement.
- Single 12-lead ECG will be obtained.
- Blood samples will be collected for laboratory assessments (clinical chemistry and hematology) and serum pregnancy test (WOCBP).
- C-SSRS to assess suicidal risk, ideation, and behavior will be completed.
- Daily maintenance and breakthrough pain opioid dosing regimens will be asked about and recorded on the appropriate eCRFs.
- Use of enema rescue medication since Visit 4 will be recorded.
- Use of concomitant medication (including bisacodyl and other laxative medication with the exception of enema) since Visit 4 will be recorded.
- AEs since Visit 4 will be recorded.

# Table 1

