#### Table 2Study drug

### 5.5.2 Doses and treatment regimens

Patients will receive study drug during the 12-week treatment period of the study (Days 2 to 85). Patients will be instructed to take 1 tablet from each bottle 1 hour before eating in the morning.

NKTR-118 or placebo will be administered once daily, as 2 tablets. Patients will receive NKTR-118 12.5 mg, or 25 mg, or placebo, as specified in Table 3.

NKTR-118					
Treatment day	12.5 mg/day	25 mg/day	Placebo		
Days 2 to 85	1 x 12.5 mg NKTR-118 tablets	1 x 12.5 mg placebo tablets	1 x 12.5 mg placebo tablets 1 x 25 mg		
	1 x 25 mg placebo tablets	1 x 25 mg NKTR-118 tablets	placebo tablets		

Table 3Administration of investigational product

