# 6.9.2 OIC Healthcare Resource Utilization Form

Opioid-induced constipation related healthcare resource utilization data will be collected at Visit 2 (Week 4), Visit 4 (Week 12), and Visit 5 (Week 14) through patient interviews. If a patient is taken off the study as a result of a resource utilization (eg, an emergency room [ER]

visit for manual disimpaction), the data should be recorded in the OIC healthcare resource utilization form prior to discontinuation. A health care resource utilization form will be used to collect information on whether the patient had any contact or visited with a health care provider (physician or other health care practitioner, urgent care center or hospital ER, or inpatient hospital) for the management of their OIC, including the details of the type and number of visits, as well as the reason for the visit (such as the use of enemas, manual disimpaction, and treatment of anal fissures).

As applicable, the interview will be conducted after the patient completes filling out the PRO questionnaires (eg, PAC-SYM, PAC-QOL, EQ-5D, NRS) in the electronic devices, and prior to any other interventions or discussions regarding the patient's OIC with the study staff or the investigator.

The PI must report medication use reported on the OIC Healthcare Resource Utilization Form (eg, enemas) on the concomitant medications eCRF. The OIC Healthcare Resource Utilization Form should not be used to report AEs but they should be reported on the AE eCRF.

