## 11.2.4 Mean bisacodyl dose per week

Bisacodyl doses will be recorded for each patient in the eCRF. The mean bisacodyl dose per week (mg) will be calculated as

(sum of bisacodyl doses (mg) during the period of interest/number of days in the period of interest) x 7.

The mean bisacodyl dose per week (mg) will be assessed for the following time intervals: enrollment to Week 4 and Week 4 to Week 12.

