## 12.2.3 Health economics

Descriptive statistics for the frequency of responses for each of the 5 EQ-5D questions will be summarized by treatment group for baseline, Weeks 4, 12, and 14. The number and percentage of questionnaires completed at each visit will also be presented.

The percentage of patients with at least 1 healthcare visit will be summarized for each OIC healthcare utilization category (physician or other health care practitioner, urgent care center or hospital ER, inpatient hospital) by treatment group. The total number of visits and number of healthcare visits per patient year will be summarized by treatment group using descriptive statistics for each OIC healthcare utilization category. In addition, the reason for the visit (eg, enemas, manual disimpactions, treatment of anal fissures, treatment of bowel necrosis, and other) will also be summarized by treatment group using descriptive statistics.

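### The OIC healthcare-visit rate counts visits through off-drug Week 14 but divides by days on drug, overstating it by about 17% at a constant visit rate for completers with Visit 5

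*Protocol*

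**What the plan says.** Section 11.6.2 defines the measure: "Healthcare resource utilization will be assessed as the number of healthcare visits per patient year for the management of their OIC", computed as "total number of visits/number of days on study drug) x 365.25". Section 12.2.3 adds: "The total number of visits and number of healthcare visits per patient year will be summarized by treatment group using descriptive statistics", for each category of care.

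Section 6.9.2 says that utilization data "will be collected at Visit 2 (Week 4), Visit 4 (Week 12), and Visit 5 (Week 14) through patient interviews". Section 3.1.3 repeats this for Day 99: "OIC Healthcare Resource Utilization questionnaire will be completed". Neither 11.6.2 nor 12.2.3 restricts the visits counted to those made while on drug.

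Dosing is fixed in Section 5.5.2: "Patients will receive study drug during the 12-week treatment period of the study (Days 2 to 85"). The synopsis places the follow-up visit two weeks after the last dose. Section 3.1.2.2 lets patients who are not continuing go back to any suitable constipation regimen after Visit 4. Table 1, footnote b, excuses patients entering the 52-week study from Visit 5.

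Section 6.9.2 requires the form at Visit 2, but the Visit 2 procedure list in Section 3.1.2 does not include it.

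**The concern.** A rate needs the same observation window above and below the line. Here the numerator can include visits from the two weeks after dosing, and the denominator stops at the last dose. The bias can only be upward.

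Two features make it more than a harmless common scale factor. It applies only to patients who have Visit 5, so its size in an arm depends on how many patients do not roll over. It also assigns to on-drug time any visits made when the patient is off drug and possibly on another constipation regimen. What is at stake is the by-arm annualised rate for an exploratory objective (Section 2.3).

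A second point concerns the level of summary. Section 6.9.2 foresees patients leaving the study because of a healthcare visit that would be counted. Short exposure and having a visit may therefore be linked, and then it matters whether the arm figure is a pooled rate or a mean of per-patient rates.

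**Working it through.** The protocol states no visit rate or expected value, so there is no figure of its own to reproduce.

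**Inputs**
- Formula: Section 11.6.2.
- Days on drug for a completer: Days 2 to 85 (Section 5.5.2), so 85 − 2 + 1 = 84.
- Off-drug follow-up: Day 99 − Day 85 = 14 days (Table 1, Section 3.1.3). Both visits have a ±3-day window.
- Share of patients with Visit 5: not stated, so 0 to 100% is shown.
- Recall period of the form: not stated in Section 6.9.2. I assume the interviews together cover the time from first dose to the last interview.
- Visit rate: not stated. I assume it is constant first, then relax this.

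**1. One completer with Visit 5.** Inflation = (84 + 14)/84 = 98/84 = 1.167. One visit gives 365.25/84 = 4.35 per year by the stated formula, against 365.25/98 = 3.73 per year over the days observed. At the extremes of the visit windows the factor runs from 95/87 = 1.09 (Days 88 and 96) to 101/81 = 1.25 (Days 82 and 102).

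**2. Arm level.** If a share f of completers has Visit 5, pooled inflation = 1 + f × 14/84.

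| Share with Visit 5 | Inflation |
|---|---|
| 0% | 0% |
| 25% | 4.2% |
| 50% | 8.3% |
| 75% | 12.5% |
| 100% | 16.7% |

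If, purely for illustration, the share were 25% in one arm and 75% in another with the same true rate, the ratio of the stated rates would be 1.125/1.042 = 1.08.

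**3. Visit rate not constant.** If the off-drug rate is r times the on-drug rate, the factor for a completer with Visit 5 is 1 + r × 14/84. It is 1.08 at r = 0.5, 1.17 at r = 1 and 1.33 at r = 2. The 17% is the equal-rate value, not a hard ceiling.

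**4. Pooled rate against mean of per-patient rates.** One visit counts as 365.25/7 = 52.2 per year for a patient with 7 days on drug, and as 4.35 for a completer. Take 210 patients (630/3, assuming equal arms), 10 of them with one visit each:
- All at 84 days: mean of rates = 10 × 4.35/210 = 0.207 per year.
- One of the 10 stopped at 7 days: mean of rates = (9 × 4.35 + 52.2)/210 = 0.435 per year, and that patient supplies 57% of it. Pooled = 10/(209 × 84 + 7) × 365.25 = 0.208 per year.

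This example deliberately places a visit in a short-exposure patient. A simulation (210 patients, assumed true rate 0.50 per year, 10% dropout, no off-drug visits) shows when that matters:
- Dropout unrelated to visits: both summaries average 0.497, with SD 0.117 for the mean of rates and 0.103 pooled.
- 25% of patients with a visit stopping because of it: the mean of rates averages 0.96, the pooled rate 0.50.

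**The case against.** The best defence is that dividing by days on drug signals an on-treatment rate, and that an analysis plan could limit the numerator to match. The protocol does not say so, however. It writes out the formula, schedules collection at Week 14 and sets no limit. The defence does succeed on weight: the objective is exploratory, Section 12.2 plans no statistical testing, and the arm-level error at a constant visit rate is between nothing and about a sixth.

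Four stronger readings are tempting, and the documents do not support them.

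- **That the rate is inflated because per-patient ratios are averaged.** Section 12.2.3 can fairly be read as per-patient summaries, but it neither states averaging nor excludes pooling. Averaging alone adds noise. It inflates only if patients with short exposure are the ones with visits, which Section 6.9.2 makes plausible but does not establish.
- **That early dropouts have their rate doubled**, for example 14 days on drug plus 14 days of follow-up, 28/14 = 2. Section 5.8 gives these patients an early termination visit with the Visit 4 assessments, and a further visit only if safety results are abnormal or clinically significant. It does not expressly say that they complete the form at Visit 5.
- **That the resource-use objective becomes unreadable.** Section 12.2.3 also reports the percentage of patients with at least one visit, the total number of visits and the reasons for them. None uses this denominator.
- **That weekly bisacodyl dose has the same fault.** Section 11.2.4 uses "sum of bisacodyl doses (mg) during the period of interest/number of days in the period of interest) x 7". It does not say that a patient who stops mid-interval keeps the full-interval divisor. Unused tablets are returned at Visit 4 or early termination, so the period can end there.

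**Conclusion.** The formula as written is wrong in one definite respect: numerator and denominator cover different periods for every patient who has Visit 5. For a completer at nominal visit days the overstatement is a factor of 1.17 (1.09 to 1.25 across the visit windows), assuming a constant visit rate and a Visit 5 interview that covers the time since Visit 4. For rollover patients it is nil. By arm it is 0 to about 17%, and unequal only if rollover is unequal, which the protocol gives no means of predicting. An individual's value changes only if an OIC visit actually falls in the follow-up period.

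The pooling point is a conditional safeguard rather than a demonstrated error. The Visit 2 omission is a genuine inconsistency between Sections 3.1.2 and 6.9.2, with no shown effect on the rate; the tick marks for this form in Table 1 did not survive text extraction and cannot settle it. Overall severity is minor.

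**What to change.** 1. **Match the windows in Section 11.6.2.** Either count only visits reported through Visit 4 or early termination, divide by days on drug and show Visit 5 visits separately; or count all visits and divide by all days observed. I prefer the first, because follow-up is off drug and only part of each arm has it. An early termination interview may take place some days after the last dose, so use the dates of the healthcare visits to assign them if the form holds them.
2. **State the arm-level rate in Section 12.2.3** as total visits / total matching patient-time × 365.25, by treatment group and category of care. Any per-patient distribution can be shown beside it.
3. **Reconcile the Visit 2 procedure list** in Section 3.1.2 with Section 6.9.2, so that sites know whether the form is due at Week 4.

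The first two changes cost a few lines of text and minor programming. Visit 5 responses are already collected at their own visit, so separating them needs no new data. With matched windows the inflation factor becomes 1.00.
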